### **Unanticipated Adverse Device Effects**

For device studies, part 21 CFR 812.3(s) uses the term unanticipated adverse device effect which is defined as any serious adverse effect on health or safety or any life-threatening problem or death caused by, or associated with the device, if that effect, problem, or death was not previously identified in nature, severity, or degree of incidence in the investigational plan or application (including a supplementary plan or application), or any other unanticipated serious problem associated with a device that relates to the rights, safety, or welfare of subjects.

 Syneron Medical Ltd. Confidential	Clinical Study to Evaluate the Safety and Efficacy of the SlimShape Device for Abdominal Fat and Circumference Reduction			
	Protocol #	DHF22621	Rev. Date	October 8, 2017

Significant device failure may constitute an adverse event if an undesirable experience occurs. This definition includes any event resulting from insufficiencies or inadequacies in the instructions for use or the deployment of the device, or any event that is a result of a user error.

**All unanticipated adverse effects will be graded as follows:**

**Mild:** Sign or symptom, usually transient, non-life-threatening requiring no special treatment and generally not interfering with usual activities.

**Moderate:** Sign or symptom, non-life-threatening which may be ameliorated by simple therapeutic measures, and may interfere with usual activity.

**Major:** Sign or symptom that is intense or debilitating but non-life-threatening and that interferes with usual activities. Recovery is usually aided by therapeutic measures and the discontinuation of the study device may be required.

**Severe:** Any untoward medical occurrence that at any time results in death or life-threatening illness, resulting in persistent or significant disability/incapacity.

**The relationship of the adverse effect to the study is defined as follows:**

**Probable:** An adverse event has a strong temporal relationship to study device, and another etiology is unlikely or significantly less likely.

**Possible:** An adverse event has a strong temporal relationship to the study device, and an alternative etiology is equally or less likely compared to the potential relationship to study device.

**Probably not:** An adverse event has little or no temporal relationship to the study device and/or a more likely alternative etiology exists.

**Not related:** An adverse event has no temporal relationship to study device or has a much more likely alternative etiology.

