## 5. Subject improvement and satisfaction:

Improvement and satisfaction assessment will be performed independently by the subject using a pre-defined scale questionnaire. The subjects will answer this questionnaire at each follow-up visit (4wk FU, 8wk FU and 12wk FU)

 Syneron Medical Ltd. Confidential	Clinical Study to Evaluate the Safety and Efficacy of the SlimShape Device for Abdominal Fat and Circumference Reduction			
	Protocol #	DHF22621	Rev. Date	October 8, 2017

Efficacy Endpoints	Primary and secondary objectives will be measured using the next efficacy endpoints: 
 
1. Fat thickness measurements using Ultrasound device
 
2. Fat thickness measurements using Caliper
 
3. Circumference measurements of the abdominal area using Measuring Tape
 
4. Investigator satisfaction using a pre-defined scale
 
5. Subject improvement and satisfaction using a pre-defined scale
 
6. Photography
 

Safety Endpoints	
 
1. The number, severity and type of any adverse event recorded throughout the study and post treatment (immediate and delayed response)
 

Statistical Methods	Descriptive statistics will be used to present changes in the assessments along the study course. Circumference measurements and subject assessments' and satisfaction data will be analyzed using two-tailed Wilcoxon Signed Rank test and/or paired t-test (alpha=0.05) to analyze the data difference from baseline and longitudinal change.

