### **Primary Safety Endpoint**

The number, severity and type of any adverse event recorded throughout the study and post treatment (discomfort (pain), immediate and delayed response).

1. Occurrence of expected post treatment immediate response including erythema and edema and during all study period based on predefined scale (Table 4).
2. Number, severity and type of any adverse event recorded throughout the course of the study.

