### **Anticipated Adverse Effects**

Following treatment with the *SlimShape* the following local adverse effects could occur (anticipated):

- Purpura
- Blister
- Bruising
- Bullae
- Erosion
- Pain/ soreness
- First degree burn
- Second degree burn

An adverse event (AE) is any undesired clinical occurrence in a study subject as indicated by signs, symptoms, illnesses, events that develop or worsen in severity in association with the study when deemed by the Investigator to be related to use of the device or study procedures. The Investigator will document all adverse signs and symptoms regardless of severity or frequency that are either volunteered by subjects or observed during the course of the study that are related to the device. The Investigator will also record adverse experiences of subjects resulting from concurrent illnesses, reactions to concurrent medications, or progression of disease states that the Investigator deems related to the device. Included in the description will be the nature of the sign or symptom, the date of onset, whether the event was serious, the severity, the relationship to study procedures or investigational device, the action taken, the date of resolution, and the outcome. The Principal Investigator will determine the relationship of the adverse device effect to the investigational device.

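### The causality scale lets weak timing alone place a delayed effect in the treated area in Probably not, although the safety endpoint names delayed response

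*Combined protocol and SAP*

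**What the plan says.** The Adverse Events chapter of the protocol defines four levels of relationship to the device.

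- The highest level, *Probable*, is worded: "An adverse event has a strong temporal relationship to study device, and another etiology is unlikely or significantly less likely".
- The level below it, *Possible*, sets the same condition of strong timing, but asks only that the other cause be no more likely than the device.
- The third level, *Probably not*, joins its two conditions with and/or: "An adverse event has little or no temporal relationship to the study device and/or a more likely alternative etiology exists".
- The lowest level, *Not related*, is met if timing is absent altogether, or if another cause is much more likely.

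No time window says what strong or little timing means, and location in the treated area is not a criterion. Under Anticipated Adverse Effects the judgement is assigned: "The Principal Investigator will determine the relationship of the adverse device effect to the investigational device".

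The Primary Safety Endpoint section covers "The number, severity and type of any adverse event recorded throughout the study and post treatment (discomfort (pain), immediate and delayed response". The safety endpoint row of the synopsis (Table 1) also names "any adverse event recorded throughout the study and post treatment (immediate and delayed response".

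The protocol defines an AE twice. The opening of the Adverse Events chapter counts any adverse change during participation. The text under Anticipated Adverse Effects counts an occurrence only when the investigator judges it related to the device or the study procedures.

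**The concern.** The endpoint asks for delayed responses, while the scale treats closeness in time as a necessary condition for the two upper classes. Suppose a site finds a new local change inside the belt area at the 8- or 12-week visit and can think of no other cause. Unless the investigator is willing to call that timing strong, Probable and Possible are both closed, and one of the two lower classes is all that remains. Where the event lies, and how implausible other causes are, cannot change this.

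Two things are at stake. The first is attribution: a table of AEs by relationship could show late local effects as probably unrelated for no reason other than when they appeared. The trial has one arm, so there is no concurrent control rate against which such under-attribution would show. The second is recording: under the narrower AE definition, a low rating could mean that the event is never entered as an AE.

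The classes also overlap, so up to 10 sites could rate identical events differently and all be following the text.

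**Working it through.** The plan states no figure here, so there is none to reproduce. The check applies the four definitions literally.

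**Inputs.** Timing has three levels (strong, little, none). The alternative cause has five (unlikely, less likely, equally likely, more likely, much more likely). An alternative that is significantly less likely is put in the unlikely level. This gives 3 × 5 = 15 combinations.

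**Rules as written.**
- Probable: strong timing AND alternative unlikely.
- Possible: strong timing AND alternative no more than equally likely.
- Probably not: little or no timing OR alternative at least more likely (the and/or).
- Not related: no timing OR alternative much more likely.

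**Result** (P = Probable, Po = Possible, PN = Probably not, NR = Not related).

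| Timing | Unlikely | Less likely | Equally likely | More likely | Much more likely |
|---|---|---|---|---|---|
| Strong | P, Po | Po | Po | PN | PN, NR |
| Little | PN | PN | PN | PN | PN, NR |
| None | PN, NR | PN, NR | PN, NR | PN, NR | PN, NR |

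**Reading the table.**
1. Less than strong timing covers 2 × 5 = 10 combinations. None reaches Possible or Probable.
2. Of those 10, 2 × 3 = 6 have no more likely alternative cause. Timing alone puts them in a lower class. The 3 with little timing meet Probably not only; the 3 with no timing meet both lower classes.
3. Every event that meets Probable also meets Possible (1 combination). Every event that meets Not related also meets Probably not (5 with no timing, plus 2 with a much more likely cause under strong or little timing, making 7). So 1 + 7 = 8 of 15 combinations fit two classes.
4. Every combination fits at least one class, so the present scale is complete. Its faults are the role given to timing and the overlap.

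**Where late events can be seen.** Return Visits places the three follow-up visits at 4, 8 and 12 weeks after the last treatment, each ±7 days. That is from 28 − 7 = 21 days to 84 + 7 = 91 days after it.

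**The case against.** The strongest reply is that nothing forces the low rating. The scale does not equate delayed with little or no timing, and the investigator could regard onset some weeks after treatment as strong timing. That stands. A reader might infer that a late local effect must be classed as unrelated; the text supports only that it can be rated low.

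A reader might also infer that weak timing alone yields Not related. It does not. By timing, that class needs no temporal relationship at all, and little timing leads only to Probably not. The two lower classes are distinct, and no section says they will be pooled in analysis.

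Next, the endpoint counts any AE, and the opening AE definition takes no account of relationship. On those sections a late event is counted whatever its rating, and no analysis restricted to related events is specified. Other sections point the same way: the Safety paragraph under Data Analysis records all complications, Return Visits requires a skin assessment at each follow-up visit, and the reporting section has unanticipated events reported to the sponsor with no relatedness threshold in that sentence. The existence of a Not related class itself implies that unrelated events are recorded somewhere. All this stands, and it confines the effect to attribution unless the narrower AE definition is applied. But that definition is in the protocol and conflicts with the rest, so loss of an event from the record cannot be ruled out.

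Finally, 12 of the nominal 16 weeks (75%) fall after the last treatment, and a reader might take that as the share of events affected. It is calendar time only. An event first seen at 4 weeks may have begun within days of treatment, and the date of onset is recorded. Nor does any section say that follow-up runs to 12 weeks in order to catch late effects; its stated purpose is device performance and fat and circumference reduction.

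**Conclusion.** The point holds as a defect in a stated rule. Without strong timing, a treated-area effect with no more likely cause cannot reach Possible. It can be rated Probably not, or Not related if timing is judged absent. That fits poorly with an endpoint that names delayed response. The overlap between classes is a second, smaller fault, since Probable and Possible are both ratings toward the device.

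The size can be given only in terms of the scale: 0 of 10 combinations with less than strong timing reach an upper class, and 8 of 15 meet two classes. How many events this touches depends on a late-event rate that the documents do not give, and on how investigators read strong timing. The conclusion rests on a literal reading of the and/or and the or. Any effect on the event count, as distinct from attribution, rests further on sites using the narrower AE definition. The change should be made, but the defect does not by itself invalidate the safety endpoint.

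**What to change.** Reword the four classes in the protocol and on the AE form so that each event fits exactly one. Changing the and/or to and would not do: strong timing with a more likely cause (1 combination) and little timing with no more likely cause (3) would then have no class, 1 + 3 = 4 of 15. A complete set is:

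- *Not related*: onset before the first treatment, or a much more likely alternative cause. Apply this class first; the other three are for the remaining events.
- *Probably not*: an alternative that is more likely but not much more likely; or an event outside the treated area with little or no temporal relationship and no much more likely alternative.
- *Possible*: strong timing with an alternative that is equally or only somewhat less likely; or an event in the treated area with less than strong timing and no more likely alternative.
- *Probable*: strong timing and an alternative that is unlikely or significantly less likely.

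For events with onset from the first treatment on, location doubles the grid to 30 combinations. Inside the treated area they fall as 1 Probable, 8 Possible, 3 Probably not and 3 Not related (15). Outside it they fall as 1, 2, 9 and 3 (15). None is left over and none falls in two classes.

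Reconcile the two AE definitions so that all AEs are recorded and counted whatever their rating.

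The cost is a few words in the protocol and on the form. The downside is that a few more late local events will be reported as possibly related.

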## **SlimShape Treatment Procedure**

### General Treatment Instructions

1. Place the patient so that he/she is lying on his/her back, with the legs extended. In this position, the abdomen is fully accessible and treatment can be easily performed.
2. Remove any jewelry in the area of the application site.
3. Ensure that the subject skin in the entire treatment is clean. The skin should be cleaned with water and soap and hairs that exist in the treatment areas will be shaved.
4. Ensure that the applicator belt is clean or wipe with 70% alcohol and allowed to dry.
5. The choice of treatment settings should take into consideration not only the severity of the treated condition (fat layer), but also the subject's skin type, tendency to bruise, the specific anatomical location (abdomen), and comfort.
6. Immediately prior the treatment, apply a generous amount of the commercial VelaEase treatment lotion, RF coupling lotion. You may need to re-apply the lotion if required.
7. Position the SlimShape Applicator Belt at the correct/ chosen treatment area (on the abdomen).
8. There should be a complete seal between the applicator and the skin during the treatment session. If you hear air being sucked into the chamber, this indicates that the contact between the skin and the belt chambers is not ideal for vacuum creation. This usually means that the applicator is not positioned properly at that moment, which tends to happen in curved or bony areas, so special attention is required when treating such areas. Changing the orientation of the applicator slightly may solve this problem.
9. The applicator belt chambers should have equal compression/contact with the skin to ensure safe and effective RF delivery.
10. Secure the magnetic pads on the sides of both belts, on both sides of the patient and tight the SlimShape belt.
11. Select the desired treatment protocol.

 Syneron Medical Ltd. Confidential	Clinical Study to Evaluate the Safety and Efficacy of the SlimShape Device for Abdominal Fat and Circumference Reduction			
	Protocol #	DHF22621	Rev. Date	October 8, 2017

12. Full operating procedure, software screens and parameters are described in the device user manuals and instruction will be provided prior to the start of the study.
13. Expected post treatment side effects are limited to Erythema (blanchable/non-blanchable), Edema, Heat sensation, Hematoma and Pain sensation.

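### The causality scale rates adverse events against the device only, although the adverse-event definition also covers study procedures, so harm from a procedure can be rated as unrelated

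*Combined protocol and SAP*

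**What the plan says.** Under Anticipated Adverse Effects, an event counts as adverse if it develops or worsens "in association with the study when deemed by the Investigator to be related to use of the device or study procedures". The same paragraph lists what must be described for each event, including "the relationship to study procedures or investigational device". Its recording sentences are narrower. The investigator documents signs and symptoms volunteered by subjects or "observed during the course of the study that are related to the device", and records effects of concurrent illness or medication only where these are judged device-related. The paragraph closes: "The Principal Investigator will determine the relationship of the adverse device effect to the investigational device".

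The causality scale that follows is headed as a relationship to the study, but each of its four categories (*Probable*, *Possible*, *Probably not*, *Not related*) is worded against the study device. The last is defined as "An adverse event has no temporal relationship to study device or has a much more likely alternative etiology".

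Table 2, in its safety row, asks for the relation to treatment. The sentence that opens the Adverse Events section defines an adverse event as any adverse change in health during participation, with no relatedness condition.

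The General Treatment Instructions make several steps part of each session besides the energy delivery. Item 3 requires washing, and shaving where hair is present. Item 6 tells the operator to "apply a generous amount of the commercial VelaEase treatment lotion, RF coupling lotion". Exclusion criterion 11 rules out subjects allergic to a component of the study lotion.

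**The concern.** The definition asks one causality question and the scale answers another. An investigator who believes that a skin reaction came from shaving or from the lotion is told that it is an adverse event because a study procedure caused it. The only scale available then has no category for that cause. On its wording, the procedure can be taken as an alternative etiology that pulls the rating away from the device.

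The study has one arm, so no comparator would show that events rated as unrelated were in fact produced by taking part. Any summary of treatment-related harm rests on these ratings, and this misattribution works in the device's favour. With up to ten sites, the same event could also be rated differently from one investigator to the next.

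**Working it through.** No arithmetic applies: the plan gives no figure on this point and no rate of procedure reactions. The check sets the places side by side and then applies the scale.

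**Step 1. Related to what?**

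| Place | Referent |
|---|---|
| Adverse Events, opening definition | none; any adverse change in health |
| Anticipated Adverse Effects, definition | device or study procedures |
| Same, recording of signs and symptoms | device |
| Same, recording of effects of concurrent illness, medication or disease progression | device |
| Same, items to describe | study procedures or device |
| Same, last sentence | device |
| Causality scale, heading | study |
| Causality scale, all four categories | device |
| Table 2, safety row | treatment |
| Primary Safety Endpoint | none; any recorded adverse event |

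Four referents (device, procedure, treatment, study) serve one rating, and the paragraph under Anticipated Adverse Effects is inconsistent within itself.

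**Step 2. Apply the scale to a shaving injury.** It arises close in time to device use, so the limb of *Not related* that requires no temporal relationship is not met. The rating then turns on how likely the other cause is:

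- shaving equally or less likely than the device: *Possible*;
- shaving more likely: *Probably not*;
- shaving much more likely: *Not related*.

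Where the investigator is confident that shaving was the cause, the lower two categories fit best. Neither records that the study caused the harm.

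**Step 3. Apply it to a lotion reaction.** The result depends on reading. If the lotion counts as part of device use, the event can be rated *Possible* or *Probable*. If it counts as a separate procedure, Step 2 applies.

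**Step 4. Follow the event to the endpoint.** The Primary Safety Endpoint counts the number, severity and type of any adverse event recorded. It sets no causality filter, and nothing elsewhere excludes events rated *Not related*. A recorded event therefore stays in whatever its rating.

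**Step 5. Ask whether it is recorded.** The opening definition would capture it. The two recording sentences under Anticipated Adverse Effects would not, if the investigator judges the procedure and not the device to be the cause. An event left out at this stage cannot be counted in Step 4. Post Treatment Procedures has visible and palpable immediate responses scored around each treatment, which covers an early reaction. A contact reaction that develops and fades between visits depends on the adverse-event record.

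**The case against.** The strongest reply is that capture regardless of cause is stated several times. Besides the opening definition, Post Treatment Procedures asks for every visible and palpable immediate response and any adverse event before, during and after treatment. The Safety paragraph under Data Analysis has all complications recorded from the start of the study. The reporting section requires unanticipated events to be reported with no relatedness test, and a lotion dermatitis is not on the anticipated list. Table 2 adds skin examination and subject interview. A reader might infer that an event rated *Not related* drops out of the safety endpoint. The documents do not support that, for the reason in Step 4. What remains is the conflict in Step 5: the same protocol gives sites both a broad and a narrow recording rule.

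The second reply is that a procedure reaction need not be rated *Not related*. That is correct: it is one possible rating among three.

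The third is that the lotion may belong to the device. It is described as an RF coupling lotion, Supply and Disposition of Study Device has it supplied alongside the device as a coupler agent, and the text on device failure extends to events arising from instructions for use, deployment or user error. This reading is reasonable, but it is not stated. It does not reach shaving as clearly, although shaving applies only where hair is present.

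None of these replies supplies a category for a procedure as cause.

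**Conclusion.** The mismatch is real and is on the face of the protocol. The definition and the list of items to describe cover device and procedures, while the scale covers the device only. A procedure-caused harm can be rated *Probably not* or *Not related* although the study caused it, which understates treatment-related harm in a single-arm study. Whether such an event is also missing from the endpoint is conditional: it requires a site to follow the device-only recording sentences over the opening definition, and is most plausible for delayed reactions.

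The size cannot be stated. The documents give no incidence of lotion or skin-preparation reactions and define no related-event rate. A reader might be tempted to contrast a related-event rate of zero with a rate that includes such reactions. That contrast would rest on an assumed incidence and on a baseline the protocol itself contradicts, since it anticipates bruising, blisters, pain and burns from the device. No sample-size or power figure is affected. The conclusion assumes only that washing, shaving and lotion application are study procedures, with the lotion open to either reading.

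**What to change.** Three passages need to be aligned.

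1. In the causality scale, rate each event against the study device and against a study procedure, with procedures stated to include the coupling lotion, skin preparation and measurements. Add a CRF field for which applies, and report both as treatment-related in the safety summary.
2. Under Anticipated Adverse Effects, bring both recording sentences and the closing sentence on the Principal Investigator's determination into line with the opening definition of the section. All adverse events are then recorded regardless of causality and rated against device and procedure. Changing the scale alone would leave the recording gap open.
3. In the safety row of Table 2, use the same referents as the scale.

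The cost is protocol wording and one CRF field. The downside for the sponsor is a possibly slightly less favourable count of treatment-related events.
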